Cover Page for Protocol

Official Study Title:	Kangaroo Care in the Operating Room
NCT Number:	NCT07223775
Document Date:	09/15/2023

University of Kansas Medical Center
RESEARCH PROTOCOL INVOLVING HUMAN SUBJECTS
TEMPLATE WITH GUIDANCE

Version date: 9/15/2023

Principal Investigator: [name] MD

Study Title: Kangaroo care in the operating room

Co- Investigator(s): [name] MD

I. Purpose, Background and Rationale

A. Aim and Hypotheses

1. Immediate and continuous skin-to-skin contact between mother and baby has been proven to improve the health of both parties. It is standard practice at KU to place the baby immediately on the maternal chest after a vaginal delivery. However, after cesarean birth the baby is first taken to the warmer for assessment and then may or may not be brought to maternal chest after several minutes. There have been good studies looking at kangaroo care (aka immediate skin to skin) during vaginal deliveries, but studies looking at this practice in the OR are lacking. There have been a few small studies that prove it's feasible.
2. Aim: Assess the maternal and infant benefits of kangaroo care in the OR. Randomize women to receive standard OR fetal resuscitation versus immediate skin to skin after scheduled cesarean deliveries of term, singletons. Hypothesis: 1- Immediate skin-to-skin (StS) during cesarean section will decrease the number of pain and anxiolytic medications required during surgery, decrease the maternal rating of pain during cesarean section, and increase the maternal satisfaction score of cesarean section. 2- There will be no difference in the 5-minute Apgar score, neonatal admission to the ICU, maternal infection rate, or QBL between the two groups.

B. Background and Significance

1. Study Significance: We anticipate that our study will demonstrate that Kangaroo care in the OR is safe, feasible and has similar benefits to mom and baby as seen with vaginal deliveries. We hope the study protocol will make everyone feel more comfortable with the practice of immediate StS in the OR. The goal would be to change the nursery protocol for baby resuscitation after cesarean deliveries allowing for standard immediate StS with benefits to mom and baby.
1. Several obstetricians currently working at KU have shared positive experiences with immediate StS after cesarean deliveries performed at other institutions. More and more patients are requesting "gentle cesarean" deliveries because they are educated about the benefits of immediate StS. When proposing we implement this process at KU, we realized there was a paucity of research around kangaroo care in the operating room. The study comes from our team's desire to improve obstetric care and encourage other institutions to do the same.

2. Literature Review: In 2016, Cochrane published a systematic review looking at if skin-to-skin contact improved breastfeeding rates and helped babies adjust to the outside world. They looked at the results of 46 studies which included almost 4000 mothers and their babies. Overall, their review supports the use of skin-to-skin to encourage breastfeeding. The evidence suggests that early skin-to-skin should be normal practice for healthy newborns including those born by caesarean and babies born early at 35 weeks or more.

Immediate and continuous skin-to-skin contact between mother and baby encourages the infant to adjust to life outside the womb. Research shows skin-to-skin results in:

- Higher axillary temperatures and lower risk for hypothermia
- Higher blood glucose levels and lower risk for hypoglycemia
- More stable respiratory rates
- Faster return to physiologically normal heart rate
- Decreased crying
- Decreased anxiety for birthing parent
- Increased self-confidence in mother's parenting ability
- Stimulation of maternal oxytocin to enhance uterine contractions, access to colostrum and mother-baby bonding – allows mother and baby to smell and feel each other
- Encouragement of breastfeeding - the warmth, smell and closeness to the breast are associated with easier and longer breastfeeding

A review article by J. Stevens et al. summarized findings of 7 studies showing that with appropriate collaboration skin-to-skin contact during cesarean surgery can be implemented. These studies also showed trends toward the above benefits which are well documented after vaginal deliveries.

C. Rationale

1. The research clearly supports the practice of immediate skin to skin after vaginal birth; therefore, we anticipate this intervention to have similar benefits after cesarean birth. KUMC is a designated Baby-Friendly hospital. The Baby-Friendly designation process requires verification of policies, curriculum, action plans, quality improvement projects, staff training, and competency verification, as well as a readiness interview and an on-site survey. When implementing immediate StS after vaginal deliveries, the healthcare providers went through training which included techniques to educate and prepare parents. Immediate StS is now standard for all vaginal deliveries at KUMC.
2. Kangaroo care in the OR is understudied and therefore this project will hopefully advance our understanding and comfort with this procedure.
3. We anticipate that implementing immediate StS after cesarean deliveries will benefit both moms and babies.

II. Research Plan and Design

A.Study Objectives: Aim: Assess the maternal and infant benefits of kangaroo care in the OR. Randomize women to receive standard OR fetal resuscitation versus immediate skin to skin after scheduled cesarean deliveries of term, singletons. Hypothesis: Immediate skin-to-skin (StS) during cesarean section will decrease the number of pain and anxiolytic medications required during surgery, decrease the maternal rating of pain during cesarean section, and increase the maternal satisfaction score of cesarean section. We hypothesize there will be no difference in the 5-minute Apgar score, neonatal admission to the ICU, maternal infection rate, or QBL between the two groups.

B.Study Type and Design: Randomized controlled trial (RCT).

C.Randomization will be done by simple randomization. Subjects will be assigned into two groups A and B. Subjects will be assigned to each group purely randomly for every assignment. Randomization will be performed by using an excel file, available here in a read only state: <http://cafe.naver.com/easy2know/6427>. Allocation concealment will be done with sealed envelopes.

1. Blinding of the physicians, nurses, and study participants is not possible in this study. We do plan to blind the statistician to the treatment. (S)he will not know the treatment name because the treatment name will be hidden, as in A and B.
2. Approximately 300 scheduled, term singleton cesareans are performed annually at KU. Our primary outcome is to detect at 20% difference in satisfaction with the procedure. Power calculation as below:
 - Total n=112 (56 per group)
 - Assumptions
 - o Alpha=0.05 (95% confidence interval)
 - o Beta=0.20 (80% power)
 - o Control group mean (SD) satisfaction 4.0 (1.5)
 - o Experimental group mean (SD) satisfaction 4.8 (1.5)

D. Subject Criteria (See Vulnerable Populations appendix, if applicable): All patients presenting for delivery at KUMC will be considered as study subjects regardless of race, age, or primary language.

1. Inclusion criteria: All term, singleton scheduled cesarean sections occurring at KUMC.
2. Exclusion criteria: Priority, urgent and emergent cesareans. Planned general anesthesia, fetal anomalies, fetal aneuploidy/genetic syndrome, abnormal fetal dopplers, placental previa, placenta accreta, multiple gestations, preeclampsia with severe features.
3. Withdrawal/Termination criteria: Standard fetal resuscitation protocols will be utilized. There are times where the infant will be brought to the warmer for infant or maternal indications. Examples of infant indications are abnormal vital signs. Maternal indications would include uncontrolled pain or surgical complication.
4. Our patients can be enrolled in studies that involve collection of cord blood after delivery. No studies are currently going on that impact the mode of delivery or infant resuscitation.

E. Specific methods and techniques used throughout the study

1. Laboratory tests: Likert scale for maternal satisfaction and pain scores. Anesthesia record will be analyzed for medications given to mom both before, during and after the cesarean delivery as part of the procedural care. Fetal apgars, skin to skin timing and NICU admission will be obtained from the pediatric nursing records.
2. Study Procedures: Standard, preexisting neonatal resuscitation protocols already in use at KUMC.
3. Routine neonatal care will be utilized in both the control (baby to warmer, delayed StS) and treatment (baby to maternal chest, immediate StS) groups.

F. Risk/benefit assessment:

1. Physical risk - none anticipated
2. Psychological risk – Our current standard of bringing the baby to the warmer after cesarean birth is hypothesized to result in more maternal anxiety compared to the treatment group receiving immediate StS.
3. Social risk - none anticipated
4. Economic risk - none anticipated
5. Potential benefit of participating in the study
 - a. The chance to be randomized to receive immediate StS with newborn and gain the known benefits associated with kangaroo care.
 - b. A change in standard practice to improve maternal and newborn care.
 - c. Published literature or poster presentation may encourage other institutions to consider immediate StS after cesarean delivery.

G. Location where study will be performed: KUMC labor and delivery.

H. Collaboration (with another institution, if applicable): n/a

I. Single IRB Review for a Multi-site study (if applicable): n/a

J. Community-Based Participatory Research (if applicable) – n/a

K. Personnel who will conduct the study, including:

1. Indicate, by title, who will be present during study procedure(s): Routine care will be performed by the physician, nurses, and techs at KUMC.
2. Primary responsibility for the following activities, for example:
 - a. Determining eligibility: PI
 - b. Obtaining informed consent: Clinical Research Coordinator
 - c. Providing on-going information to the study sponsor and the IRB: PI
 - d. Maintaining participant's research records: Clinical Research Coordinator
 - e. Completing physical examination: the physicians performing cesarean delivery as part of standard care.
 - f. Taking vital signs, height, weight: the nurses and physicians providing routine care to mom and newborn.
 - g. Drawing / collecting laboratory specimens: the nurses and physicians providing routine care to mom and newborn.

- h. Performing / conducting tests, procedures, interventions, questionnaires: the nurses and physicians providing routine care to mom and newborn.
- i. Completing study data forms: the nurses and physicians providing routine care to mom and newborn.

Managing study database: PI and Clinical Research Coordinator.

L. Assessment of Subject Safety and Development of a Data and Safety Monitoring Plan

- 1. n/a – no more than minimal risk. As per routine care, if StS is determined to be unsafe based on maternal or baby status, it will be terminated at the request of the obstetrician or newborn nurse based on the same standards we use for routine StS practice.
- 2. If adverse events happen with routine care, they will be reported to the PI and communicated to the IRB. As with any adverse healthcare events, a safety incident (SI) report will be generated by KUMC staff.

III. Subject Participation

A. Recruitment:

- 1. Any patients who deliver at KUMC and meet inclusion criteria will be recruited. These patients may or may not have received prenatal care at KUMC. The obstetricians on staff at KUMC also provide the prenatal care for women at Vibrant Health and Johnson County Health Department. These patients will be included in our research study. We also perform cesarean deliveries for maternal fetal medicine and family medicine patients.
- 2. The study coordinator will review the L&D OR schedule to identify cases that meet study criteria. Our study coordinator will then call the patients to review the study with them. When feasible, the study coordinator can also come to clinic to recruit patients during their routine prenatal care visits. Lastly, if a patient presents to L&D for a scheduled cesarean but has not been recruited during their prenatal care, they will be introduced to the study while on labor and delivery.
- 3. Advertisements - n/a
- 4. Recruitment letter - n/a

- B. Screening Interview/questionnaire:** Chart review will be used at the primary means of screening for inclusion/exclusion criteria.

C. Informed consent process and timing of obtaining of consent

- 1. During prenatal care, it will be the research coordinator. Informed consent will be performed over the phone or in person. Over the phone consent will utilize Redcap or in person a printed document will be signed by the patient. If a patient presents to L&D for her scheduled, term singleton cesarean delivery without having been informed of the study, she will be informed by the Clinical research coordinator.
- 2. Personnel involved in the consenting process include the study approved clinical research coordinators. All people involved in consenting patients will be trained in the principals of medical informed consent.
- 3. No one is consented under duress. Only scheduled, planned cesareans are included in the study.

- D. Alternatives to Participation:** Routine care will be conducted.

E. **Costs to Subjects:** n/a

F. **How new information will be conveyed to the study subject and how it will be documented:** MyChart(electronic health record) message to study participants.

G. **Payment, including a prorated plan for payment:** n/a

H. **Payment for a research-related injury:** n/a

IV. **Data Collection and Protection**

A. **Data Management and Security:**

1. Redcap and Heron. Only the PI and other research personnel identified on the IRB application.
2. All collected information will be de-identified. A code with subject numbers and their corresponding MRNs will be kept in an excel spreadsheet on the P drive.
3. Participants will be assigned a subject number, not identified by name/dob/mrn.
4. The research coordinator will keep the excel spreadsheet code on the p drive.
5. The patient's assigned research participant number (as assigned by the research coordinator after recruitment) will be included in the research tab in the electronic health record. This participant number will be used when the subject's data is entered into redcap survey.
6. Data stored in redcap survey.
7. Mobile devices - n/a
8. No data sent outside KUMC

B. **Sample / Specimen Collection:** n/a

C. **Tissue Banking Considerations:** n/a

D. **Procedures to protect subject confidentiality:** n/a

E. **Quality Assurance / Monitoring**

- 1.Data taken from the electronic health record will be used.
- 2.No third-party monitoring.

V. **Data Analysis and Reporting**

A. **Statistical and Data Analysis:** Participant demographics will be summarized using descriptive statistics (proportions and means). Differences between study groups will be assessed using chi-square and t-tests for categorical and continuous variables, respectively. Differences in satisfaction and pain scores between study groups will be assessed using t-tests if the data is normally distributed. If not normally distributed, data will be adjusted by taking the log of the mean scores, or a non-parametric comparison of medians will be conducted. If any clinically important differences exist between the experimental and control groups at baseline, a linear regression model will be constructed allowing us to control differences between groups.

B. **Outcome:** Primary outcome is maternal satisfaction. Improvement in maternal satisfaction with the cesarean delivery will be the criteria for success. We set clinically meaningful difference of 20% improved satisfaction.

C. **Study results to participants:** none

D. **Publication Plan:** Our goal is to publish our RCT in either AJOG or ACOG journals.

VI. Bibliography / References / Literature Cited (choose the applicable title and list citations according to APA or other accepted style in your discipline)

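### The no-difference hypothesis for Apgar, NICU admission, infection and QBL has no margin or confidence-interval rule, so a non-significant result cannot support it

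*Combined protocol and SAP*

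**What the plan says.** Sections I.A and II.A both state the second hypothesis as equality: "We hypothesize there will be no difference in the 5-minute Apgar score, neonatal admission to the ICU, maternal infection rate, or QBL" between the groups. Section I.B.1 attaches an expected conclusion: "We anticipate that our study will demonstrate that Kangaroo care in the OR is safe, feasible and has similar benefits to mom and baby" as after vaginal delivery. The same paragraph names a change to the nursery's resuscitation protocol as the goal.

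Section V.A first says that demographics will be summarised. It continues: "Differences between study groups will be assessed using chi-square and t-tests for categorical and continuous variables, respectively". It then gives satisfaction and pain their own sentence (t-tests, a log transformation or a non-parametric comparison). It ends with a linear regression if clinically important baseline differences appear. Apgar, NICU admission, infection and QBL are not named there.

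Section II.C.2 derives 112 women, 56 per group, from satisfaction alone. Section V.B makes improved satisfaction the criterion for success. Nowhere do the documents give a margin, an equivalence or non-inferiority test, a confidence-interval rule, an expected event rate or a power statement for any hypothesis 2 outcome.

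**The concern.** A test of difference can reject equality but cannot establish it. A large p-value arises when the groups are alike, and also when the sample is too small to tell. Under the plan as written, the only result that could be offered in support of hypothesis 2 is a non-significant one. For uncommon binary events in 112 women, that result is likely even if the true risk has doubled.

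At stake is the safety statement that would accompany a positive satisfaction result. A proposal to change newborn care after cesarean will be judged partly on NICU admission and infection. Section II.L marks the data and safety monitoring plan as not applicable, so the end-of-study comparison is the only between-group look at safety that the documents imply.

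**Working it through.** **Inputs.** From II.C.2: 56 per group, alpha 0.05, power 80%, satisfaction means 4.0 and 4.8, SD 1.5. The protocol gives no event rates for NICU admission or infection and no SDs for QBL or Apgar. Control rates of 2%, 5% and 10% are therefore assumed, and continuous outcomes are expressed in SD units.

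**1. The plan's own figure.** n per group = 2(1.96 + 0.842)² × 1.5² / 0.8² = 55.2, rounded up to 56, so 112 in total. The stated number reproduces with a two-sided test. It is right for satisfaction and was not chosen for safety.

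**2. Power for binary outcomes.** For each pair of true rates, the binomial probabilities of all outcomes (i of 56, j of 56) with Pearson |z| > 1.96 were summed, where z = (j/56 − i/56) / √[p̄(1 − p̄) × 2/56] and p̄ = (i + j)/112. The last column is the total sample size for 80% power (normal approximation).

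| Assumed control rate | Doubled rate | Exact Pearson power | Total N for 80% power |
|---|---|---|---|
| 2% | 4% | 7% | 2282 |
| 5% | 10% | 16% | 870 |
| 10% | 20% | 32% | 398 |

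Across this range a true doubling is missed at least two times in three.

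**3. What the interval would still allow.** Newcombe's interval combines the Wilson limits of the two arms.
- 0/56 versus 0/56: the Wilson upper limit is 1.96²/(56 + 1.96²) = 3.84/59.84 = 6.4%. The 95% interval for the risk difference is ±6.4 points.
- 2/56 versus 2/56: the Wilson limits are 1.0% and 12.1% around 3.6%. The half-width is √(8.55² + 2.59²) = 8.9 points.
- 6/56 versus 1/56 (10.7% versus 1.8%): Pearson p = 0.051. The difference is 8.9 points, with a 95% interval from −0.6 to +19.8. This six-fold observed excess would be non-significant.

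**4. Continuous outcomes.** The 95% half-width for a mean difference is 1.96 × √(2/56) = 0.37 SD. With no true difference, the margin that could be excluded with 80% power is (1.96 + 0.842) × √(2/56) = 0.53 SD.

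**5. Margins that 112 women could support for binary outcomes.** With equal true rates p, one-sided 2.5% and 80% power, the margin is 2.80 × √[2p(1 − p)/56]. This gives about 7, 12 and 16 percentage points at 2%, 5% and 10%.

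**The case against.** The strongest reply is that no trial decision depends on hypothesis 2. Success is defined by satisfaction, the sample size is correct for that outcome, and the safety expectation sits in the significance section, not the analysis plan. All of this stands. It limits the point to the secondary safety claim.

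Three stronger readings are tempting, and the documents do not support them.

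- *That the plan will treat p > 0.05 as proof of safety.* No section states such a rule. The risk is inferred from a hypothesis of equality, an expectation of demonstrating safety, and the absence of any analysis that could support either. Nor is it certain that chi-square and t-tests are the planned analysis for these outcomes. The sentence follows the one on demographics and may cover baseline variables only. In that case the safety outcomes have no stated analysis, and the same repair is needed.
- *That the design can say nothing about any of the four outcomes.* QBL and Apgar would be estimated to about 0.37 SD. At low event rates, a wide margin for the binary outcomes would also be within reach (step 5). For these the gap is the missing margin. The power argument bears mainly on NICU admission and infection.
- *That chi-square is invalid at these counts and Fisher's test should replace it.* Expected counts would often fall below 5, but that rule is a convention. By the enumeration in step 2, with equal true rates of 2%, 3%, 5% and 10%, the Pearson test's actual type I error is 1.7%, 3.3%, 4.5% and 5.0%. It is not inflated. Fisher's is 0.06%, 0.25%, 0.9% and 2.0%, and its power for 5% versus 10% is 8% against 16%. Switching would make a missed harm more likely.

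**Conclusion.** The concern holds in a limited form. Hypothesis 2 asserts no difference, yet the plan contains nothing that could support that assertion: no margin, no interval rule, and a sample sized for another outcome. For NICU admission and infection, 112 women give roughly 7% to 32% power to detect a doubling at assumed control rates of 2% to 10%. Observing no events at all would still leave a difference of 6.4 points open. These sizes depend on the assumed rates. The logical gap does not, and it applies equally to QBL and Apgar despite their better precision.

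The primary analysis, the sample size and the success criterion are unaffected. This should be fixed, but it does not threaten the trial's main result.

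**What to change.** - **I.A and II.A:** replace hypothesis 2 with an objective to estimate the between-group differences in 5-minute Apgar, NICU admission, maternal infection and QBL, each with a two-sided 95% confidence interval.
- **V.A:** name these outcomes. Specify Newcombe or Miettinen-Nurminen intervals for the binary ones, and a mean difference with confidence interval for QBL and Apgar. State that p > 0.05 will not be reported as no difference or as safe, and that such a claim will be made only if the interval lies within a margin fixed before unblinding.
- **I.B.1:** say that the study will describe safety outcomes, in place of demonstrating safety.

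The cost is some rewording and a few lines of analysis code, with no extra participants. The downside is a more modest safety claim. If the investigators want a formal one, they must justify a margin for each outcome and check the sample size against it.

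### Allocation relies on a web-hosted Excel file and loosely specified envelopes, with no independent allocator and no link to the day of surgery; central electronic allocation would protect concealment better at little cost

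*Combined protocol and SAP*

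**What the plan says.** Section II.C contains the whole allocation procedure. The method is unrestricted: "Randomization will be done by simple randomization", and "Subjects will be assigned to each group purely randomly for every assignment". The source is described thus: "Randomization will be performed by using an excel file, available here in a read only state", followed by an external web address. Concealment has one sentence: "Allocation concealment will be done with sealed envelopes". Item 1 of the same section adds: "Blinding of the physicians, nurses, and study participants is not possible in this study". The statistician is the exception ("We do plan to blind the statistician to the treatment"), with the groups coded A and B.

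Other sections show who does what, and when:

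- II.K.2: the PI determines eligibility and the clinical research coordinator obtains consent. No one is named for generating, holding or releasing the sequence.
- III.A.2: the coordinator searches the operating-room schedule for cases and telephones the women.
- III.C.1: consent may be taken during prenatal care, by telephone or in person ("Over the phone consent will utilize Redcap"), or on labor and delivery for women not approached before.
- IV.A: the coordinator assigns subject numbers after recruitment and keeps the file linking them to medical record numbers.
- IV.E.2: there is no third-party monitoring.
- II.D.2: priority, urgent and emergent cesareans are excluded.

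**The concern.** In an unblinded trial, concealment of the next assignment is the main protection against selective enrolment. Blinding the statistician protects the analysis but does nothing at the point of entry.

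There is motive and room for selection here. Section I.B reports obstetricians' favourable experience with immediate skin-to-skin contact and growing patient demand for it. Section II.C.2 puts scheduled term singleton cesareans at about 300 a year, against 112 places. The primary outcome is the mother's own satisfaction rating, which a prior preference could plausibly influence. If someone recruiting could learn or guess the next assignment, women keen on the intervention could be steered towards it. The regression in V.A adjusts for observed baseline differences, and no measure of preference is planned, so this bias could not be removed afterwards.

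Timing is a second exposure. If the envelope is opened at a prenatal consent, the delivery may later become urgent and so meet an exclusion criterion after randomisation. Section V.A defines no analysis population to say how such a woman is handled.

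**Working it through.** **1. What the text settles and what it leaves open**

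| Element | Stated | Not stated |
|---|---|---|
| Sequence | Excel file at an external web address, read-only | Whether the file is this trial's list or a general tool; who generates the list; whether a fixed copy is kept |
| Envelopes | Sealed | Opaque, numbered, logged; who prepares and holds them |
| Separation of roles | PI: eligibility. Coordinator: screening, consent, numbering | Any person outside enrolment who controls allocation |
| Timing | Consent possible in prenatal care or on labor and delivery | When the envelope is opened; whether eligibility is checked again first |
| Oversight | No third-party monitoring | Any other check on envelope handling |

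If the linked file is the list, anyone with the protocol could look up assignments. If it is a generator, the assignments become fixed only once sealed, and the plan requires no audit copy of what was generated. Both readings fit the text. Under either one, protection rests on envelope handling that is not described and on people who also enrol.

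**2. Room for selection**

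112 / 300 = 37% of one year's scheduled term singleton cesareans, before exclusions and refusals. There would be considerable scope to choose whom to approach. How far that scope would be used cannot be derived from the documents.

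**3. Does simple randomisation harm the sample size?**

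Inputs from II.C.2: means 4.0 and 4.8, SD 1.5, alpha 0.05, power 80%. Assumptions: a two-sided test (this reproduces the stated total; one-sided would give 44 per group) and 1:1 assignment (implied by the equal planned groups).

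- The plan's figure: n per group = 2 × (1.960 + 0.842)² × 1.5² / 0.8² = 2 × 7.85 × 2.25 / 0.64 = 55.2, rounded up to 56, so 112 in total. This is reproduced.
- Power at 56/56: SE = 1.5 × √(1/56 + 1/56) = 0.2835; 0.8 / 0.2835 − 1.960 = 0.862; power 80.6%. Based on the t distribution it is 79.9%.
- Group size under simple randomisation: Binomial(112, 0.5), SD = √112 / 2 = 5.3. P(exactly 56/56) = 7.5%; P(gap of 10 or more) = 39.5%; P(gap of 20 or more) = 7.2%. Both groups lie within 46 to 66 with probability 95.3%.
- Power at 46/66: SE = 1.5 × √(1/46 + 1/66) = 0.2881; 0.8 / 0.2881 − 1.960 = 0.817; power 79.3% (t-based 78.6%).
- Power averaged over all splits, weighted by their binomial probabilities: 80.2% (t-based 79.5%).

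The expected loss is 80.6 − 80.2 = 0.4 points (t-based 79.9 − 79.5 = 0.4). At 46/66 it is 80.6 − 79.3 = 1.3 points. Perfect balance would recover only these amounts.

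**The case against.** The strongest reply is that sealed envelopes are a recognised concealment method, that the protocol names them, and that silence about opacity, numbering and custody does not show these safeguards are absent. That stands, and it limits the point to how the method is set up. It does not remove the point, because a stronger arrangement is cheap and the plan names no one outside enrolment to run the present one.

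A reader might infer more from the text in four places:

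- *That the allocation list is publicly posted.* The protocol never says the linked file holds this trial's sequence. Assignments made at random one by one would also fit a generating tool, and the file itself cannot be seen from the documents.
- *That concealment fails.* Nothing shows a breach. Sealed envelopes imply that assignments are fixed before use, so a generator could be rerun mainly before sealing.
- *That women needing urgent delivery will be lost after randomisation.* Consent is not randomisation, and the subject number is an identifier. Loss would require both early opening and exclusion from the analysis, and neither is stated. The text permits it and no more.
- *That simple randomisation is part of the weakness.* Past assignments say nothing about the next one, so it is the least predictable scheme. Unequal groups do not bias the planned comparison, and the power cost is trivial. Permuted blocks would trade some predictability for balance that is hardly needed.

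Screening mainly by chart review (III.B), with eligibility decided by the PI, limits discretion somewhat. It does not replace concealment, since it leaves open who is approached and when.

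**Conclusion.** The concern holds in a limited form. As written, concealment depends on a web file of unstated nature and on envelopes whose handling is not described, in an unblinded trial where no one independent of enrolment controls allocation and no outside monitoring is planned. The text also permits allocation well before surgery, and so the randomisation of women who later become ineligible.

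The possible bias cannot be sized from the documents. The case for change rests on three things: the bias could not be corrected in analysis, motive and room for selection are both documented, and prevention costs little. The imbalance from simple randomisation can be sized, at about 0.4 points of power on average and 1.3 points at 46/66, and is no reason to change the method. Those figures assume a two-sided test, 1:1 assignment, and all 112 women contributing data. The change should be made before enrolment goes further; this is not a finding that the trial's allocation has been compromised.

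**What to change.** 1. Replace the web file and envelopes in II.C with central electronic allocation. REDCap's randomisation module is the natural candidate, since the trial already uses REDCap for telephone consent and data storage; that the module is available at the site is an assumption to confirm.
2. If it is not available, use opaque, sequentially numbered envelopes with a log of each opening, prepared and held by someone who does not enrol.
3. Have the list generated, and uploaded where electronic, by a named person outside enrolment. Keep the seed and list as the audit record.
4. Release each allocation only after consent and after eligibility has been re-confirmed on the day of surgery, and say so in II.C and III.C.
5. Simple randomisation may stay. If blocks are preferred for balance, vary their size at random and hide the sizes from recruiters.

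The cost is set-up time and a protocol edit, plus some time from a person outside the enrolling team. The sample size and the analysis do not change.
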